The study includes a 1-week screening period and an 8-week lead-in period. In 2 of the treatment groups, LY900014 and insulin lispro will be administered immediately (0-2 minutes) prior to each meal in a double-blind manner. Patients in these groups will complete a 52-week treatment period (with primary endpoint at 26 weeks), and a 4-week safety follow-up period. A third open-label treatment group consists of LY900014 administered 20 minutes after the start of a meal (LY900014+20). Patients in this treatment group will complete a 26-week treatment period and the 4-week safety follow-up period.

All patients who complete the 4-week safety follow-up visit (Visit 801) and have treatment-emergent insulin lispro antibodies that have not returned to prespecified baseline range (Visit 2) will be asked to participate in follow-up to monitor insulin lispro antibody levels. Study visits will be scheduled at approximately 3-month intervals for up to 26 weeks from Visit 801 or until insulin lispro antibodies return to baseline range, whichever occurs sooner.

Number of Patients:

Approximately 1500 participants will be screened to achieve 1199 randomized patients and 1020 patients completing 26 weeks of treatment, with approximately 646 patients completing 52 weeks.

Statistical Analysis:

The primary analysis is for the treatment period through Week 26.

Efficacy analyses will be conducted on all randomized patients according to the treatment the patients are assigned. The analyses for the primary and multiplicity adjusted objectives will be performed for the efficacy estimand including data collected prior to permanent discontinuation of investigational product (IP) through Week 26 and for the ITT estimand (treatment regimen estimand) including all data collected through Week 26 regardless of IP use. When change from baseline is included as a response variable of analysis models, the patient will be included in the analysis only if a baseline and at least 1 postbaseline measurement are available. Selected efficacy analyses will also be conducted using the Per Protocol (PP) and Completer populations. Week 52 analyses will include the LY900014 and insulin lispro treatment arms and only be performed for the efficacy estimand.

Safety analyses will be conducted on the Safety population. Analyses of adverse events (AEs) will include 2 sets of analyses, unless otherwise specified. The first set of analyses will include data collected prior to permanent

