10.3. Statistical Analyses

10.3.1. General Statistical Considerations

Statistical analysis of this study will be the responsibility of Lilly or its designee. Any change to the data analysis methods described in the protocol will require an amendment ONLY if it

changes a principal feature of the protocol. Any other change to the data analysis methods described in the protocol, and the justification for making the change, will be described in the statistical analysis plan (SAP) or the clinical study report (CSR). Additional exploratory analyses of data will be conducted, as deemed appropriate.

The primary analysis is for the treatment period through Week 26. The primary endpoint is the HbA1c measurement obtained at Week 26 (Visit 18). The measurement obtained at Week 52 (Visit 22) will be a secondary endpoint.

Efficacy analyses will be conducted on all randomized patients according to the treatment the patients are assigned. The analyses for the primary and multiplicity adjusted objectives will be performed for the efficacy estimand including data collected prior to permanent discontinuation of IP through Week 26 and for the ITT estimand (treatment regimen estimand) including all data collected through Week 26 regardless of IP use (Section 10.3.3.1). Unless otherwise specified, the efficacy analyses for other secondary objectives and exploratory objectives will be performed for the efficacy estimand. When change from baseline is included as a response variable of analysis models, the patient will be included in the analysis only if he/she has a baseline and a postbaseline measurement. Selected efficacy analyses will also be conducted using the Per-Protocol (PP) and Completer populations. Week 52 analyses will include the LY900014 and insulin lispro treatment and only be performed for the efficacy estimand.

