10.3.3. Efficacy Analyses

10.3.3.1. Primary Analyses

The primary objective of this study is to test the hypothesis that LY900014 is noninferior to insulin lispro on glycemic control (NIM=0.4% for HbA1c) in patients with T1D, when administered as prandial insulin (0-2 minutes prior to the meal), in combination with basal insulin for 26 weeks. There will be 2 primary analysis methods, each tested at the full significance level of 0.05.

For the US FDA submission, the primary analysis method will use the copy reference approach to impute missing data based on multiple imputations with a pattern mixture model. This

analysis is for the ITT estimand that will include all data collected from randomization through Week 26, regardless of IP use. The reference will be all observed data from the randomized patients in the same treatment group who discontinue IP and complete the study without missing data. After imputation, the primary efficacy comparison will be based on the contrast between LY900014 and insulin lispro from the ANCOVA analysis of change from baseline to Week 26 in HbA1c using all randomized patients as described in Section 10.3.1.

If there are only a limited number of patients in the reference group as described above that leads to a failure in performing the proposed multiple imputation analysis, the reference will be changed to include all observed data from all randomized patients in the same treatment arm who complete the study without missing data.

For non-FDA submissions and publications, the primary efficacy comparison will be based on the contrast between LY900014 and insulin lispro at Week 26 (Visit 18) from the MMRM analysis of change from baseline in HbA1c including data collected from all randomized patients prior to permanent discontinuation of IP through Week 26 (efficacy estimand). The analysis model and selection of covariance structure are described in Section 10.3.1.

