HbA1c ANCOVA (ITT estimand)	All Randomized Patients with a baseline and at least 1 postbaseline observation	Last of Visits 7-8	Visit 18 regardless of IP use, with imputation for patients who discontinue the study prior to Visit 18
HbA1c categorical analyses longitudinal logistic regression and LOCF logistic regression	All Randomized Patients with a baseline and at least 1 postbaseline observation while on IP	Last of Visits 7-8	Visits 11, 13, 15, and 18 prior to discontinuation of IP AND Last of Visits 9-18 prior to discontinuation of IP
1-hr and 2-hr PPG and other MMTT variables (efficacy estimand)	All Randomized Patients with a postbaseline observation while on IP	Visit 8 prior to initiation of IP	Visit 18 prior to discontinuation of IP
1-hr and 2-hr PPG and other MMTT variables (ITT estimand)	All Randomized Patients with a postbaseline observation	Visit 8 prior to initiation of IP	Visit 18 regardless of IP use
10-point SMBG, basal, prandial, and total insulin doses, prandial/total insulin dose ratio	All Randomized Patients with a baseline and at least one postbaseline observation	Visit 8 prior to initiation of IP	Visits 11, 13, 15, and 18 prior to discontinuation of IP AND Last of Visits 9 to 18 prior to discontinuation of IP
1,5-AG	All Randomized Patients with a baseline and at least 1 postbaseline observation	Visit 8 prior to initiation of IP	Visits 11, 15, and 18 prior to discontinuation of IP AND Last of Visits 9-18 prior to discontinuation of IP
Health outcomes: ITSQ, CCI	All Randomized Patients with a baseline and a postbaseline observation	Last of Visits 1-8	Last of Visits 9-18 prior to discontinuation of IP
Safety Laboratory Tests (chemistry, hematology, lipids) – continuous analysis	All Patients in the Safety Population with a baseline and a postbaseline observation	Last of Visits 1-8	Visit 18 (planned) AND Last of Visits 9-18 (planned including early discontinuation), regardless of IP use
Safety Laboratory Tests (chemistry, hematology, lipids) – categorical analysis	All Patients in the Safety Population with a normal baseline (with respect to the direction being analyzed) and a postbaseline observation	Visits 1 -8 (including unplanned tests)	Visits 9 to 18 (including unplanned tests), regardless of IP use

Baseline and Postbaseline Definitions and Patient Population by Study Period and Type of Analysis

Study Period/Analysis	Patient Population	Baseline Observations	Postbaseline Observations

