Study Procedures	Lab/Imaging Criteria	Missing HbA1c at baseline/at the primary endpoint	Mixed (monitoring and clinical database)	Central laboratory data to indicate that a). HbA1c is not collected at both Visit 7 and Visit 8 or b). HbA1c is not collected at the primary endpoint (only applicable to patients who completed the primary endpoint without early discontinuation from the study).
Study Procedures	Visit Schedule Criteria		Programmable (clinical database)	CRF Subject Visit panel data to indicate that 2 consecutive office visits are completely missing.
Study Procedures	Other	Electronic Clinical Outcomes Assessment (eCOA)	Programmable (clinical database)	Comparison of patient data from CRF and eCOA to identify randomized patients who have no ed diary data entered.
Administrative/Oversight	Suspected Misconduct		Non Programmable (monitoring)	Site staff sharing account details for systems (e IWRS, EDC or ePresentOnline). Suspected falsification of data.
Safety	Safety Mailings		Non Programmable (monitoring)	Lack of, significant delay in safety mailing review (significant delay defined as a delay of 90 days).
Safety	SAEs		Non Programmable (monitoring)	Failure to report an SAE within 24 hours of the investigator being made aware of the SAE. Failure to respond to SAE queries.

Description of Important Protocol Deviations

Category	Sub-categories	Description	Source	Methods of Identification
Safety	Other	Failure to report product complaint within 24 hours.	Non Programmable (monitoring)	Identified by CRA as captured in sCTMS.

Abbreviations: # = number of inclusion/exclusion criteria in protocols; CGM = continuous glucose monitoring; CRA = clinical research associate; CRF = clinical (case) report form; CRP = clinical research physician; CRS = clinical research scientist; CT = clinical trial; HbA1c = hemoglobin A1c; ICD = informed consent document; eCOA = Electronic Clinical Outcome Assessments; EDC = Electronic Data Capture; IWRS = interactive Web Response System; MedDRA = Medical Dictionary for Regulatory Activities; SAE = serious adverse event; sCTMS = Simplicity Clinical Trial Management System; T1D = type 1 diabetes; yrs = years.

Furthermore, of the above listed important protocol deviations, the following may significantly impact the results of the primary objective:

- lack of informed consent
- have any hematological condition that may interfere with HbA1c measurement
- missing HbA1c at both Visit 7 and Visit 8, or missing HbA1c at the primary endpoint.

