6.11. Efficacy Analyses

6.11.1. Primary Outcome and Methodology

The primary objective of this study (H1) is to test the hypothesis that LY900014 is noninferior to insulin lispro on glycemic control (NIM=0.4% for HbA1c) in patients with T1D, when administered as prandial insulin (0-2 minutes prior to the meal), in combination with basal insulin for 26 weeks. There will be 2 primary analysis methods, each tested at the full significance level of 0.05.

For the US FDA submission, the primary analysis method will use the copy reference approach to impute missing data based on multiple imputations with a pattern mixture model. This analysis is for the ITT estimand that will include all data collected from randomization through Week 26, regardless of IP use. The reference will be all observed data from the randomized patients in the same treatment group who discontinue IP and complete the study without missing data. After imputation, the primary efficacy comparison will be based on the contrast between LY900014 and insulin lispro from an ANCOVA. The model for the change from baseline to the Week 26 HbA1c endpoint will include treatment and strata (pooled country, type of basal insulin, and prandial insulin dosing plan) as fixed effects and baseline HbA1c as a covariate.

If there are only a limited number of patients in the reference group as described above that leads to a failure in performing the proposed multiple imputation analysis such that the model cannot converge or the number of records without missing data is less than the number of records with missing data, the missing HbA1c measurement at Week 26 will be imputed by the patient-level observed baseline value plus a noise assuming a washout of any potential treatment effect (that is, “return to baseline”). The noise follows a normal distribution with the variability estimated from the “washout HbA1c data,” which will be derived by subtracting the corresponding treatment mean at Week 26 from individual non-missing HbA1c values at Week 26.

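### Protocol and SAP give conflicting patient sets and imputation scope for the FDA primary (ITT) HbA1c analysis; SAP Table 6.2 as written leaves out randomized patients with no postbaseline HbA1c

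*SAP*

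**What the plan says.** **Patient set.** Protocol 10.3.3.1 bases the FDA primary comparison, after imputation, on the "ANCOVA analysis of change from baseline to Week 26 in HbA1c using all randomized patients as described in Section 10.3.1". The synopsis also specifies all randomized patients. Section 10.3.1, to which that sentence points, carries a general rule for change-from-baseline models: "the patient will be included in the analysis only if he/she has a baseline and a postbaseline measurement". The synopsis has its own version: "the patient will be included in the analysis only if a baseline and at least 1 postbaseline measurement are available". In SAP 6.1, Table 6.2 sets the population for each analysis. Its row for the ITT HbA1c ANCOVA reads "All Randomized Patients with a baseline and at least 1 postbaseline observation".

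**Imputation scope.** The same row gives the endpoint as "Visit 18 regardless of IP use, with imputation for patients who discontinue the study prior to Visit 18". SAP 6.3 refers HbA1c imputation to 6.11.1. That section applies copy-reference multiple imputation to missing data. If this fails, "the missing HbA1c measurement at Week 26 will be imputed by the patient-level observed baseline value plus a noise". Neither rule is confined to patients who leave the study.

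**Patients in the study without the endpoint.** SAP Table 6.3 lists as an important protocol deviation that "HbA1c is not collected at the primary endpoint (only applicable to patients who completed the primary endpoint without early discontinuation from the study". The plan therefore foresees patients who reach Week 26 without a Visit 18 HbA1c.

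**The concern.** An ITT analysis with imputation is meant to keep every randomized patient in the comparison. Requiring a postbaseline HbA1c makes inclusion depend on follow-up after randomization, so randomization no longer fully protects the contrast. The exclusion is also unnecessary, because the return-to-baseline rule needs only the patient's own baseline.

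Two analysts could build different data sets in good faith, one from Table 6.2 and one from protocol 10.3.3.1 with SAP 6.11.1. This analysis decides H1 and also supplies H4 (HbA1c superiority) and H5 (noninferiority of the postmeal arm). The planned sensitivity analyses do not bring the excluded patients back: the Per Protocol and Completer sets (SAP 6.11.3) are narrower, and the delta stress test (SAP 6.11.4) changes only values that were imputed. The fallback in 6.11.1 is triggered partly by comparing the number of records with and without missing data, so who belongs to the set also enters that decision.

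**Working it through.** **1. Compare the rules for three kinds of patient, each with a baseline HbA1c.**

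| Patient | Protocol 10.3.3.1 | Protocol 10.3.1 / synopsis general rule | SAP Table 6.2, ITT row | SAP 6.3 and 6.11.1 |
|---|---|---|---|---|
| Left the study, no postbaseline HbA1c | in, imputed | out | out | Week 26 value is missing, so imputed |
| Left the study, some postbaseline HbA1c, no Visit 18 value | in, imputed | in | in, imputed | imputed |
| Still in the study, earlier HbA1c present, no Visit 18 value | in, imputed | in | meets the population definition; no imputation mentioned | imputed |

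The first row is a direct conflict, and it runs through the protocol as well as the SAP. The third is an inconsistency within the SAP. For the first row, return to baseline needs only the baseline value. Copy reference could presumably work from baseline too, but 6.11.1 does not list the imputation-model variables, so that is an inference.

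**2. Reproduce the planned sample size** (protocol 10.1, SAP 5.2). Inputs: SD 1.1, true difference 0, 371 completers per double-blind arm, two-sided 95% CI.
- Standard error = 1.1 × √(2/371) = 0.0808.
- Power = Φ(margin/SE − 1.96): 99.86% at 0.4 (plan: at least 99%) and 96.0% at 0.3 (plan: 95%).
- 371/0.85 = 436.5 (plan: 436); 436 + 436 + 327 = 1199; 1199 × 0.85 = 1019 (plan: 1020).

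The plan's figures reproduce, and none of them depends on the disputed set.

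**3. How many patients could lack a postbaseline HbA1c?** The documents do not say. The first scheduled postbaseline HbA1c is Visit 11, Week 4. Assume that the 15% loss occurs at a constant hazard.
- Weekly hazard h = −ln(0.85)/26 = 0.00625.
- Lost before Week 4 = 1 − exp(−4h) = 0.0247.
- 0.0247 × 1199 = 29.6 patients; 0.0247 × 436 = 10.8 per double-blind arm.

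The Schedule of Activities also has HbA1c at the early-discontinuation visit and Visit 801. The ITT row does not say whether those samples count as postbaseline. If they do, the number falls. If losses are concentrated early, it rises. A range of 1% to 5% is 12 to 60 of 1199.

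**4. Possible shift in the contrast** (assumed inputs).
- Exclusion differs by 2 percentage points between arms, and those patients do 0.5 to 1.0 points worse: 0.02 × 0.5 to 0.02 × 1.0 = 0.01 to 0.02.
- Equal exclusion of 1% to 5%, with the excluded patients' mean change differing between arms by 0.4 to 1.0: 0.01 × 0.4 to 0.05 × 1.0 = 0.004 to 0.05.
- For scale, the 95% CI half-width with 436 per arm is 1.96 × 1.1 × √(2/436) = 0.146, a standard error of 0.0745.

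A shift of 0.02 is about a quarter of a standard error (0.02/0.0745 = 0.27). The extreme corner, 0.05, is about a third of the half-width (0.05/0.146 = 0.34).

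**5. Power.** Treating imputed values as fully informative, which is an upper bound, 436 per arm gives 99.97% at 0.4 and 98.1% at 0.3. Removing 1% to 5% leaves at least 99.9% at 0.4 and 97.5% to 98.0% at 0.3.

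**The case against.** The strongest reply is that the SAP has not departed from the protocol. The protocol states the baseline-plus-postbaseline rule twice, and the sentence in 10.3.3.1 about all randomized patients itself points to 10.3.1. This stands. A reader might infer that the SAP breaks a clear protocol promise, but the protocol contradicts itself and Table 6.2 carries over one side.

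A second reply is that in-study patients without a Visit 18 HbA1c are not excluded. With an earlier value they meet the row's population definition, the row does not say that imputation is only for discontinuers, and 6.3 and 6.11.1 cover any missing Week 26 value. This also stands. A reader might infer that these patients are simply dropped; the documents show inconsistent handling, not a stated exclusion. The documents give no rate for such patients either, so adding an allowance for them to the early leavers would have no source.

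Third, early leavers may be few: protocol 5.3.1 asks anyone leaving the study early to complete the early-discontinuation visit, which includes HbA1c. This limits the size but does not settle which set is meant.

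Finally, one might conclude that patients still on investigational product need their own missing-at-random imputation. That would be a debatable change to the FDA primary method and does not follow from the inconsistency. None of these replies removes the conflict over patients with no postbaseline HbA1c.

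**Conclusion.** Wrong as written. For the FDA primary ITT analysis, the protocol and SAP between them specify two patient sets and two imputation scopes. Under Table 6.2, randomized patients with no postbaseline HbA1c are left out although their Week 26 value could be imputed.

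The affected number is unknown. About 2.5% (30 of 1199) is the figure under a constant hazard and 15% loss if early-discontinuation samples do not count; it is lower if they do. The likely shift of 0.01 to 0.02 HbA1c points rests on assumed differences between arms. It is small beside the 0.4 margin and would matter, if at all, only for a borderline H4 result. Nothing here shows that a conclusion would change, and power is not the issue. The reason to act is that the patient set behind H1, H4 and H5 should have one reading, fixed before unblinding, that does not depend on post-randomization follow-up.

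**What to change.** - **SAP Table 6.2, ITT HbA1c row.** Population: all randomized patients with a baseline HbA1c. Endpoint: the Visit 18 value whether or not the patient is on investigational product, with every missing Visit 18 HbA1c imputed under Section 6.11.1 whatever the reason.
- **Protocol 10.3.1 and synopsis.** Exempt this analysis from the postbaseline-measurement rule.

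A patient without a baseline HbA1c (none at Visit 7 or Visit 8) would still be left out. That condition is fixed before randomization and does not raise the same difficulty.

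The imputation methods in 6.11.1 stay as they are. The cost is a wording change in one SAP row and an exemption to a rule stated in two places in the protocol, a few more imputed records, and possibly a slightly wider confidence interval.
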